### 5.6.2. Primary Efficacy Endpoint

Primary endpoint is the change in total contusion volume (hematoma plus perihematomal edema) as measured by brain imaging from baseline to 96 hours or prior to DC, IPH evacuation or CMO if these procedures occur before 96 hours per the central review. The definition of main estimand follows a white-on-treatment strategy [ICH E9 (R1) Addendum, 2020], i.e., all the central reads between 12 hours after the initiation of study drug infusion and Hour 96 or prior to DC, IPH evacuation or CMO if these procedures occur before 96 hours will be used; see details in Section [3.4.1](#).

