¹⁰ The optional blood sample for pharmacogenetic analysis requires a separate informed consent form to be administered between the start of study and hospital discharge. The pharmacogenetic sample should be collected as close to the consenting procedure as possible and preferably within 24 hours of the start of study treatment. The date and time of collection should be recorded.

¹¹ A delayed intubation eCRF must be completed if a participant is intubated for deteriorating neurologic status.

¹² Hourly (\pm 30 minutes) for Hour 0 to Hour 24, every 2 hours (\pm 30 minutes) for Hour 25 to Hour 48, and every 4 hours (\pm 60 minutes) for Hour 49 to Hour 96. If treatment for low BG (< 70 mg/dL [\sim 3.9 mmol/L]) is initiated, then BG monitoring is required every 15 minutes (\pm 10 minutes) until BG is \geq 80 mg/dL (\sim 4.4 mmol/L) for 3 consecutive readings without exogenous bolus glucose supplementation. See Section 11.4.1.1.1 for details on BG monitoring and management.

¹³ [REDACTED] A CMO eCRF must be completed for participants for whom care is withdrawn.

¹⁴ An NCCT scan is sufficient for participants who cannot get an MRI.

¹⁵ The 96 hour scan should be performed after study treatment infusion is complete, within 18 hours of the Hour 96 time point.

¹⁶ Only required if ET occurs before the Hour 96 scan has been performed.

¹⁷ Includes all AEs from the beginning of study treatment administration and all SAEs from the time of consent. AEs of special interest (hypoglycemia [BG < 55 mg/dL (\sim 3.1 mmol/L)]) will be upgraded to an SAE. See Section 15.3 for further details on monitoring and recording AEs.

¹⁸ A short suicidal ideation/behavior questionnaire will be conducted on participants who are alert and capable of providing answers at Screening (prior to dosing). For these participants, this questionnaire should be repeated at Days 30, 90, 180, and ET Visit. The questionnaire conducted at Screening will record “Life Time” events and subsequent visits (at Days 30, 90, 180, and ET Visit) will record “Since the Last Visit” events.

CONFIDENTIAL

The information contained herein may not be used, disclosed, or published without the written consent of Biogen MA Inc.

Table 3: ECG, [REDACTED] Schedule of Activities

	12-lead ECG¹	
Predose	SOC ECG taken at Screening	
Minute 5	±5 minutes	
Hour 6	±5 minutes	
Hour 24	±5 minutes	
Hour 48	±5 minutes	
Hour 72	±5 minutes	
Hour 96	±5 minutes	

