7. STUDY DESIGN

7.1. Study Overview

This is a Phase 2, randomized, multicenter, double-blind, multidose, placebo-controlled study to assess the efficacy and safety of BIIB093 in inhibiting the progression of traumatic intracerebral contusions in participants aged 18 to 85 years.

Approximately 60 sites in 7 countries globally are planned. The study will randomize 160 participants.

Participants must be treated with BIIB093 within 10 hours of time of trauma/LKN and within 6 hours of hospital arrival. Dosing should be initiated within 1 hour of randomization and continue for 96 hours (4 days). For participants in the 3 mg/day dose arm, treatment will be initiated similarly to the regimen in an ongoing Phase 3 study targeting edema associated with LHI. Participants will receive a bolus IV dose of 0.13 mg (given over approximately 2 minutes), followed by 2 different infusion rates (a rapid IV infusion of 0.1644 mg/h for 6 hours followed by a slow IV infusion of 0.1134 mg/h for the remaining 90 hours). In the 5 mg/day dose arm, participants will receive a bolus IV dose of 0.21 mg (given over approximately 2 minutes), followed by 2 different infusion rates (a rapid IV infusion of 0.2722 mg/h for 6 hours followed by a slow IV infusion of 0.1871 mg/h for the remaining 90 hours). These treatment rates should be administered within the limitation of the device at the site. The treatment duration will be for 96 hours for both treatment groups.

The primary endpoint of this study will be the change in total contusion volume (hematoma plus perihematomal edema) as measured by brain imaging from baseline to 96 hours, or prior to DC, IPH evacuation, or CMO, if these procedures occur before 96 hours.

[figure not shown]
Participants will also have the functional assessments (i.e., GOS-E, [REDACTED], and mRS) performed at both Day 90 and Day 180 post trauma.

After the last participant completes their Day 4 (Hour 96) Visit, data for the primary endpoint and available data for the secondary endpoints will be locked for analysis. The final database lock will occur after the last participant completes their Day 180 Follow-up Visit, marking the end of the study.

See Figure 1 for a schematic of the study design.

CONFIDENTIAL

The information contained herein may not be used, disclosed, or published without the written consent of Biogen MA Inc.

Figure 1: Study Design

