11.2. Modification of Dose and/or Treatment Schedule

The dosage should not be modified unless due to hypoglycemia (sustained BG < 55 mg/dL [~ 3.1 mmol/L]). In the event of hypoglycemia, the study treatment infusion rate must be reduced as presented in [Table 4](#).

Table 4: Dose Modification Schedule

If hypoglycemia occurs within the first 6 hours of infusion:	
For participants on high infusion rate (0.2722 mg/h)	The infusion rate must be reduced to 0.1644 mg/h. If hypoglycemia cannot be rectified or reoccurs, the infusion rate must be further reduced to 0.0795 mg/h and must not be uptitrated.
For participants on low infusion rate (0.1644 mg/h)	The infusion rate must be reduced to 0.0795 mg/h and must not be uptitrated.
If hypoglycemia occurs after the first 6 hours of infusion:	
For all study participants	The infusion rate must be reduced to 0.0795 mg/h. The infusion rate can be uptitrated to 0.1134 mg/h when blood glucose is > 80 mg/dL (~ 4.4 mmol/L) for 3 consecutive readings.

If, at the reduced rate (0.0795 mg/h), hypoglycemia cannot be rectified by the treating team and the severity and length of hypoglycemia is determined by the Investigator to be harmful to the participant, treatment should be discontinued (see [Table 5](#) for further details).

If the study treatment needs to be temporarily stopped due to SOC ICU activities (e.g., transport of patient, IV-line changes or interstitial extravasation, etc.), the study treatment should be restarted as soon as possible per instructions in the DHA.

The infusion period will not be extended to account for any stoppages or reduction.

For mitigation strategies for hypoglycemia associated with dosing, please see [Table 5](#).

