16.2. Efficacy

16.2.1. Analysis Population

The primary efficacy analyses will be conducted in the modified intent-to-treat population, which is defined as participants who are randomized and treated and have at least 1 centralized read of contusion volume from an NCCT or MRI scan acquired between 12 hours after the initiation of study treatment and by the Hour 96 Visit or prior to DC, IPH evacuation, or CMO, if performed before the Hour 96 visit.

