#### **3.4.1. Change in Total Contusion Volume (hematoma plus perihematomal edema) from Baseline to 96 Hours**

Total contusion volume will be assessed by the central imaging core laboratory on baseline NCCT, 24-hour NCCT, and the 96-hour scan (MRI and / or NCCT) and the scans obtained prior to DC, IPH evacuation or CMO. Change in total contusion volume (hematoma plus perihematomal edema) as measured by brain imaging from baseline to 96 hours or prior to DC, IPH evacuation, or CMO if these procedures occur before 96 hours per central review, will be derived from available central reads, at baseline (before Hour 0) and closest to Hour 96. If multiple timepoints

are applicable, the read from the visit closer to Hour 96 will be used for analysis. If both MRI and NCCT have been carried out then the MRI read will be used.

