#### **4.2. Primary Analysis**

The primary analysis will be performed after the Day 4 (Hour 96) administrative database lock when the last participant completes their study drug infusion at the Hour 96 visit. The primary analysis is used to formally evaluate the treatment effect of BIIB093 on imaging-based endpoints as well as the on-treatment safety compared with the matching placebo. It will include the analyses of primary endpoint (change in total contusion volume as defined in [Section 3.4.1](#)) and other imaging-based endpoints, and on-treatment safety data summaries. The primary efficacy and safety analyses will be performed on the full analysis set and the safety analysis set, respectively, as defined in [Section 3.6](#), unless otherwise specified in [Section 5](#).

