## **APPENDICES**

## APPENDIX 1. IMAGING DATA PER THE CENTRAL REVIEW

### *On-Protocol Images for the Central Review*

MR and NCCT images will be used to assess changes in brain contusion, hemorrhage and edema volume, [REDACTED]. Eligible participants will undergo NCCT at baseline and Hour 24 and MRI/NCCT at Hour 96.

- Screening NCCT will be the one closest to the randomization, which is assessed for eligibility with a brain contusion volume of > 3mL per investigator review and used for stratification at randomization
- All NCCT/MRI brain images collected by the imaging CRO up to the Hour 96 visit (or NSx or CMO, if earlier) will be considered on-protocol images and will be submitted for central review

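### The SAP gives conflicting upper time limits for the primary-endpoint scan and does not say which one governs

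*SAP*

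**What the plan says.** **When the scan is due.** Footnote 15 to Table 2 in protocol Section 5, repeated in SAP Appendix 2, reads: "The 96 hour scan should be performed after study treatment infusion is complete, within 18 hours of the Hour 96 time point". Protocol 7.1 fixes the infusion length ("The treatment duration will be for 96 hours for both treatment groups"), and protocol 11.2 rules out lengthening it ("The infusion period will not be extended to account for any stoppages or reduction"). SAP 3.1 counts study hours from the start of the infusion. The Hour 96 column of the Schedule of Activities carries a general tolerance of ±12 h.

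**Which reads count.**
- SAP 5.6.2, which defines the main estimand, uses "all the central reads between 12 hours after the initiation of study drug infusion and Hour 96", or reads before decompressive craniectomy, hematoma evacuation or comfort measures. It refers to 3.4.1 for details.
- SAP 3.4.1 works from the available central reads and, where several qualify, says "the read from the visit closer to Hour 96 will be used for analysis". It states no upper limit.
- SAP 3.1 maps efficacy data from scheduled and unscheduled visits with Table 1. For volume data, the Hour 96 window there is 76 to 116 h and the Hour 24 window is 10 to 38 h.

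**Which scans define the analysis set and go to central review.**
- Protocol 16.2.1 requires at least one read from a scan "acquired between 12 hours after the initiation of study treatment and by the Hour 96 Visit".
- SAP 3.6.1 has the same upper limit but starts at 10 h.
- SAP Appendix 1 classes as on-protocol "All NCCT/MRI brain images collected by the imaging CRO up to the Hour 96 visit", or up to surgery or comfort measures if earlier.

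**The concern.** A site that follows footnote 15 after a full infusion produces a scan later than the cut-off written into the estimand. It may also produce one later than the visit limit that decides which images are on-protocol. The scan concerned supplies the primary endpoint. SAP 3.4.4 takes the 96-hour edema volume from the same follow-up visit, so that secondary endpoint inherits the problem.

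If a late scan is excluded, the SAP does not say clearly what replaces it. The nearest-to-Hour-96 rule in 3.4.1 has no lower bound of its own, so an Hour 24 NCCT read could become the 96-hour value. Otherwise the value is missing. Protocol 16.2.2.2 calls for multiple imputation of missing Hour 96 values, but SAP 5.6.2 does not mention it. The first outcome changes what is being measured; the second costs information.

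There is also a pre-specification issue. Protocol 9.3 has an unblinded sponsor team run both the interim and the primary analyses. Choosing between cut-offs at that stage would be an analyst's choice on the primary endpoint, made with treatment codes available.

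**Working it through.** **Inputs.** Infusion: 2-minute bolus, then 6 h, then 90 h (protocol 4.5.1 and 7.1). Scan tolerance: 18 h (footnote 15). Visit tolerance: ±12 h (Schedule of Activities). Volume window: 76 to 116 h (SAP Table 1). Design: difference 15 mL, SD 29 mL, 80 per pooled group, two-sided 5% t-test (protocol 16.8, SAP 2.3).

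**Scheduled interval.** The infusion ends at 2/60 + 6 + 90 = 96.03 h. The latest scheduled scan is at 96 + 18 = 114 h. A participant with a full infusion is therefore due at about Hour 96 to 114, an 18 h interval.

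**Overlap of each rule with Hour 96 to 114.** Accepted hours = min(upper limit, 114) − max(lower limit, 96), and not below 0.

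| Rule | Window (h) | Accepted | Share |
|---|---|---|---|
| SAP 5.6.2, literal | 12 to 96 | 96 − 96 = 0 | 0% |
| Hour 96 visit at ±12 h | 84 to 108 | 108 − 96 = 12 | 12/18 = 67% |
| SAP Table 1, volume data | 76 to 116 | 114 − 96 = 18 | 100% |
| SAP Table 2 (non-efficacy data) | 84 to 120 | 114 − 96 = 18 | 100% |

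The ±12 h reading leaves out Hour 108 to 114, which is 6/18 = 33% of the permitted interval. That is a share of hours, not of participants.

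**The plan's power figure.** With noncentrality 15 / (29 × √(2/n)), n = 80 gives 15 / 4.585 = 3.27 and a t-test power of 90.2% (90.5% by normal approximation). The stated figure of approximately 90% is reproduced.

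**What losing Hour 96 values would cost.** The documents give no scan times, so the share lost is purely an assumption. The values are treated as simply missing, and equally so in both groups.

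| Assumed share lost | n per group | t-test power |
|---|---|---|
| 0% | 80 | 90.2% |
| 5% | 76 | 88.7% |
| 10% | 72 | 86.9% |
| 20% | 64 | 82.7% |
| 33% | 53 | 75.1% |

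The 33% row would match the ±12 h reading only if scan times were spread evenly over Hour 96 to 114. The table does not cover the other outcome, in which an earlier read replaces the 96-hour value. In that case n stays the same and the endpoint changes.

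**The case against.** The strongest reply is that the SAP already has a governing rule. SAP 3.1 says efficacy data analyzed by visit are mapped with Table 1, and its window covers the whole scheduled interval. SAP 5.6.2 hands the detail to 3.4.1, which has no upper cut-off. The primary objective counts the 96-hour scan itself, so a rule that shuts it out would contradict the endpoint. Footnote 15 is attached to the imaging cell and, being specific, should prevail over the ±12 h column header. Protocol 13.1 has the 96-hour scan read centrally, and protocol 19.1.5 sends all imaging to the core laboratory.

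Most of this stands. It makes Table 1 the probable intention and the literal reading of 5.6.2 an unlikely one. It does not remove the conflict. No sentence gives Table 1 precedence over 5.6.2, 3.6.1 or Appendix 1. Table 1 can also only place reads that exist: SAP 3.4 derives the imaging variables from on-protocol images, and Appendix 1 ends those at the Hour 96 visit without giving an hour.

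A reader might infer more than the documents support:
- *That every on-schedule scan is lost.* This needs the literal reading of 5.6.2 with Table 1 and 3.4.1 ignored. Footnote 15 also says should, and Hour 96 to 114 applies to full infusions only.
- *That participants drop out of the modified intention-to-treat set.* One qualifying read is enough, so a usable Hour 24 scan keeps the participant in.
- *That late scans come from clinically different patients.* The Version 2 amendment summary cites MRI availability and off-hours presentation as reasons for the 18 h window. It does not cite clinical stability.
- *That the primary lock is mistimed.* SAP 4.2 does speak of the lock "when the last participant completes their study drug infusion at the Hour 96 visit", but the protocol ties it to completion of the Day 4 (Hour 96) Visit. At most this concerns the last participants, and it is minor.

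**Conclusion.** The point holds as an internal conflict in the SAP over the primary endpoint, not as an established loss of data. Three upper limits are in force: Hour 96, the Hour 96 visit and Hour 116. They accept 0, 12 and 18 of the 18 scheduled hours respectively, taking the visit as ±12 h and the infusion as run in full. Section 5.6.2 is wrong as written, because applying it literally would discard scans taken as instructed and could let an Hour 24 read stand as the 96-hour value.

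The number of participants affected cannot be derived from the documents. The power losses shown are conditional illustrations. If Table 1 is applied throughout, no on-schedule scan is lost on timing, and power stays at 90.2% with 80 evaluable per group under the plan's own assumptions. No sample-size figure is in error.

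**What to change.** Change the SAP only, before the Day 4 administrative lock and before any further unblinded analysis:

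1. In 5.6.2, replace the Hour 96 endpoint of the read interval with the end of the Hour 96 analysis window in Table 1 (Hour 116). Leave the truncation at craniectomy, hematoma evacuation or comfort measures as it is.
2. Use the same limit, in hours, in 3.6.1 and in the Appendix 1 definition of on-protocol images, in place of the Hour 96 visit.
3. Settle the lower limit in the same edit. It is 10 h in Table 1 and 3.6.1, but 12 h in 5.6.2 and protocol 16.2.1.
4. Record any resulting difference from protocol 16.2.1 in SAP Section 6, which at present lists no changes.

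The cost is a short SAP revision. It needs no new data, no change to the protocol's scan schedule (footnote 15 already governs the scan) and no change to the sample size.

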### Main Analysis

The analysis of the primary endpoint will consist in testing the null hypothesis  $H_0: p_1 = p_2$  versus the alternative hypothesis  $H_1: p_1 \neq p_2$ , where  $p_1$  is the change from baseline of total contusion volume in the placebo group and  $p_2$  that in the BIIB093 combined group according to the randomized treatment group for the full analysis set.

- The hypothesis will be tested using ANCOVA, adjusted for covariates specified in Section [5.6.1](#), at a 2-sided significance level of 0.05 with the Day 4 database.
- The estimated least squared mean difference for treatment group, the corresponding 95% confidence interval and the p-value will be reported.
- In case that the ANCOVA does not converge numerically due to perfect separation of the responses by some stratification factor, the stratification factor that causes it will be excluded from the model.

### Sensitivity Analysis and Supplementary Analysis

- A supplementary analysis on the primary endpoint will be performed on the mITT population and excluding all DC, IPH evacuation or CMO.
- A sensitivity analysis on the primary endpoint will be performed on the PP population.
- A sensitivity analysis on the primary endpoint will be performed on the mITT population using the eCRF data as covariates rather than IRT stratification data.

### 5.6.3. Secondary Efficacy Endpoints

#### GOS-E at Day 180

GOS-E will be assessed as a 7-category ordinal scale (1/2, 3, 4, 5, 6, 7, 8) at discharge, Day 30, Day 90, and Day 180.

- GOS-E at Day 180 will be analyzed by randomized treatment based on observed data for the full analysis set using ordinal logistic regression adjusting for covariates specified in Section [5.6.1](#).

- Dichotomized GOS-E (0-4 versus 5-8) at Day 180 will be analyzed using binary logistic regression adjusting for covariates specified in Section [5.6.1](#).
- Multiple imputation for missing GOS-E values at Day 180 will be conducted as specified in Section [5.1](#). The analysis results from imputed datasets will be combined for inference using Rubin's rule.
- Descriptive statistics for GOS-E scores will be summarized by visit (see Section [5.1](#)).

### **mRS at Day 90**

mRS will be assessed at Day 90 and Day 180 as a 5-category ordinal scale (0/1, 2, 3, 4, 5/6).

- mRS at Day 90 will be analyzed in the final database for the full analysis set using ordinal logistic regression based on observed data adjusting for covariates specified in Section [5.6.1](#).
- Dichotomized mRS (0-2 versus 3-6) at Day 90 will be analyzed using binary logistic regression adjusting for covariates specified in Section [5.6.1](#).

### **Proportion of Participants Requiring Delayed Intubation**

Proportion of participants who required delayed intubation for neurologic deterioration at any time between 24 hours and 96 hours postinjury or LKN will be analyzed for the full analysis set in the Day 4 database.

- The proportion of participants requiring delayed intubation will be analyzed using binary logistic regression adjusting for covariates specified in Section [5.6.1](#).

### **Change in Total Contusion Volume from Baseline to 24 Hours**

Change in total contusion volume from baseline to 24 hours or prior to DC, IPH evacuation or CMO if these procedures occur before 24 hours per central review will be analyzed in the Day 4 database for the full analysis set.

- ANCOVA will be performed to compare the mean change between BIIB093 combined and placebo groups based on the observed data.
- By-visit mean and change in total contusion volume from baseline will be summarized.

### **Change in Absolute Hematoma Volume from Baseline to 24 Hours**

Change in absolute hematoma volume from baseline to 24 hours will be analyzed in the Day 4 database for the full analysis set.

- ANCOVA will be performed to compare the mean change between BIIB093 combined and placebo groups based on the observed data.
- By-visit mean and change in absolute hematoma volume from baseline will be summarized.

### Change in Absolute Edema Volume from Baseline to 96 Hours

Change in absolute edema volume from baseline to 96 hours will be analyzed in the Day 4 database.

- ANCOVA will be performed to compare the mean change between BIIB093 combined and placebo groups based on the observed data.
- By-visit mean and change in absolute edema volume from baseline will be summarized.

[figure not shown]
## Time to All-cause Death, Including Neurological Death, through Day 90

Survival time in days through Day 90 is defined as the time from randomization to death, including all-cause death and neurological death. For a participant who discontinues and is not known to have died during the study, survival time will be censored at the time when the participant is last known to be alive of the study. Survival time will be analyzed in the Day 90 database for all randomized participants.

- Survival time will be analyzed using Cox proportional hazards regression models of overall survival after adjusting for covariates specified in Section [5.6.1](#).
- Kaplan Meier curves of survival will be presented for BIIB093 3mg/day, BIIB093 5 mg/day, BIIB093 combined and placebo groups.

A horizontal bar chart consisting of 10 black bars of increasing length from left to right. The bars are set against a white background. The first bar is the shortest, and the 10th bar is the longest, extending almost to the right edge of the frame.

